5.2.2 Treatment Schedule

CDX-301 and CDX-1140 will only be administered to subjects on Arm 1. Subjects on Arm 2 will not “crossover” if disease progression is observed. The Study Calendar (Section 4.2) describes the timing of study drug administrations.

Some subjects on Arm 1 may receive more than one “cycle” of CDX-301, CDX-1140, and SBRT (targeting a lesion not previously treated with SBRT). The decision to administer treatment cycles beyond cycle 1 must be agreed upon by the treating physicians, the principal investigators, and the study subject. Additional treatment cycles will not be offered to subjects who develop disease progression within four months of receiving a previous cycle of study therapy or to subjects who have no evidence of active disease. Subjects who previously experienced DLT or intolerable toxicity related to CDX-1140 may be treated with CDX-301 and SBRT and without CDX-1140 in subsequent treatment cycles.

For subjects who receive more than one cycle of study therapy, the schedule of events will reset at the beginning of each cycle. At least 8 weeks must separate the start of each treatment cycle.

CDX-301

Five injections of CDX-301 should be administered daily during Week 1 (Monday-Friday) of a treatment cycle. If that is not possible due to department closure for a national holiday, inclement weather, or another reason that is not treatment-related toxicity, CDX-301 treatment may extend to Week 2 (though not beyond 10 days after the first CDX-301 dose).

CDX-1140

The first CDX-1140 will take place 4 days (+/- 1 day) after the last dose of CDX-301. As CDX-301 will typically be given from Monday-Friday, CDX-1140 will usually be given on a Tuesday. The second dose of CDX-1140 will be given 4 weeks (+/- 3 days) after the first CDX-1140 dose. CDX-1140 will not be administered on a Friday, as a clinic visit the day after each CDX-1140 dose is required.

5.2.3 Medications to be given before/after study drug administration

CDX-301

No premedication is required for CDX-301.

No medication is required after CDX-301 injections.

CDX-1140

Prophylactic premedication is required, at least 30 minutes prior to administration of CDX-1140:

- diphenhydramine 25/50 mg (or equivalent antihistamine)
- 500 to 750 mg paracetamol (acetaminophen)
- naproxen sodium 250 mg (or equivalent NSAID), at least 30 minutes prior to CDX-1140 administrations.
- Ranitidine 150 mg (or equivalent) and/or an anti-emetic (ondansetron 8 mg, or equivalent) may also be incorporated into the premedication regimen.
- Prophylactic premedication with corticosteroids is to be avoided because of the potential to attenuate the anti-tumor activity of CDX-1140.

Post-infusion medication is required over the 24-48 hours after each CDX-1140 infusion:

- Alternating oral acetaminophen (1000 mg) and non-steroidal anti-inflammatory (e.g., ibuprofen 200 mg) q6h.
- An antihistamine and anti-emetic may also be utilized if clinically indicated.
- Patients should be evaluated to determine if continuation of post-infusion medication is needed when they are seen on the Cycle 1 Day 2 visit.
- The potential for toxicity with these drugs should be recognized, and appropriate precaution should be utilized in patients with risk factors for toxicity, such as patients with peptic ulcers, increased LFTs, or increased creatinine. Also, care should be taken to medicate for no longer than is necessary, to avoid adverse events.

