4.2.2 Arm 1 (experimental study arm)

ARM 1	Week 1	Week 2	Week 4	Week 6	Weeks 9 ¹ , 17 ² , 25 ² , 33 ² , 41 ² , 49 ²
History and Physical Examination	X	X ⁵ X ⁶	X	X ⁵ X ⁶	X
CBC, BMP, LFTs, Amylase, Lipase	X	X ⁵ X ⁶	X	X ⁵ X ⁶	X
Activity Data Download ³	X	X	X	X	X
QoL Assessments		X	X	X	X
Correlative Study Blood Draw		X ⁷		X ⁷	X
CDX-301 ADA and CDX-1140 PK		X ⁷ X ⁸ X ⁶		X ⁷ X ⁶	
CT C/A/P					X
Stereotactic Radiotherapy (SBRT) ⁴	XXX				
FLT3 Ligand (CDX-301)	XXXXX				
CD40 Agonist Antibody (CDX-1140)		X		X	

1. +/- 1 week

2. +/- 2 weeks

3. For subjects who opt to participate in this part of the study

4. SBRT should be delivered in 1, 3, or 5 fractions per target and may continue beyond Week 1 when treating multiple sites.

5. On the day of CDX-1140 infusion

6. One day after CDX-1140 infusion

7. Immediately before CDX-1140 infusion

8. 2 hours after CDX-1140 infusion

Cycles of SBRT(to an untreated lesion)+CDX-301+CDX-1140 may be repeated.

- At least 8 weeks must separate the start of each treatment cycle.
- CDX-1140 may be omitted from retreatment cycles for subjects with prior DLT or intolerable toxicity attributed to CDX-1140.
- The schedule of assessments will reset when a new cycle is initiated.

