- Prophylactic premedication is required prior to CDX-1140 administration: diphenhydramine 25/50 mg (or equivalent anti-histamine), 500 to 750 mg paracetamol (acetaminophen), and naproxen sodium 250 mg (or equivalent NSAID) at least 30 minutes prior to CDX-1140 administrations. Ranitidine 150 mg (or equivalent) may also be incorporated into the premedication regimen. Prophylactic premedication with corticosteroids is to be avoided because of the potential to attenuate the anti-tumor activity of CDX-1140.
- Post-infusion medication is required following CDX-1140 administration: In the 24-48 hours following the CDX-1140 infusion, alternate oral acetaminophen (1000 mg) and non-steroidal anti-inflammatory (e.g., ibuprofen 200 mg) q6H. An anti-histamine and anti-emetic may also be utilized if clinically indicated. Patients should be evaluated to determine if continuation of post-infusion medication is needed when they are seen on the Cycle 1 Day 2 visit. Note, the potential for toxicity with these drugs and appropriate precaution should be utilized in patients with risk factors for toxicity, e.g. patients with peptic ulcers, increased LFTs, or increased creatinine. Also, care should be taken to mediate for no longer than is necessary in order to avoid

potential confounding factors in determining adverse event causality (e.g. increased LFTs).

- The effect of CDX-1140 on the absorption, metabolism, or excretion of other drugs has not been studied. As CDX-1140 is a human monoclonal antibody, inhibition or induction of cytochrome P450 (CYP) enzymes or other typical drug metabolizing enzymes is unexpected, and thus, interaction with other medications metabolized through these pathways is unlikely.
- For patients in Part 2, concomitant administration of CDX-301 with growth factors such as G-CSF should be done with caution and the CBC followed closely.

6.0 STUDY THERAPY – ARM 2

Stereotactic Body Radiotherapy for Limited Disease

Subjects on Arm 2 with “limited disease”, as defined in Section 5.1.1, will be treated with SBRT to all sites of known active disease. SBRT details are provided in Section 5.1. SBRT will be delivered in the same fashion for both study arms.

Other radiotherapy

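### Two CDX-1140 safety instructions do not fit this trial's schedule: the post-infusion medication check is set before the first infusion, and the Grade 2 rule relies on an observation period that Section 5.2.4 does not set

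*Combined protocol and SAP*

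**What the plan says.** **Post-infusion medication.** Section 5.2.3 states: "Post-infusion medication is required over the 24-48 hours after each CDX-1140 infusion". The same list fixes the review point: "Patients should be evaluated to determine if continuation of post-infusion medication is needed when they are seen on the Cycle 1 Day 2 visit". Section 5.2.7 repeats that sentence and adds that "care should be taken to mediate for no longer than is necessary in order to avoid" factors that could confound the causality of adverse events, with raised LFTs as its example.

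**Schedule.** Section 5.2.2 states: "Five injections of CDX-301 should be administered daily during Week 1 (Monday-Friday) of a treatment cycle". Then: "The first CDX-1140 will take place 4 days (+/- 1 day) after the last dose of CDX-301". The second infusion comes 4 weeks (+/- 3 days) after the first. The same section says that "a clinic visit the day after each CDX-1140 dose is required". The Arm 1 calendar in Section 4.2.2 places an examination and laboratory tests in Weeks 2 and 6 under footnote 6: "One day after CDX-1140 infusion".

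**Observation.** Section 5.2.4 has all subjects monitored for 2 hours after each CDX-1140 administration, and says so twice. Its Grade 2 instruction concerns an adverse event that arises in a 4 to 6 hour observation period and does not resolve within it. Such a subject is observed for 24 hours or until resolution, with vital signs every 4 hours. No section sets a 4 to 6 hour period.

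**Looser wording nearby.** Section 5.2.6 gives the post-infusion medication as 24 hours and makes the NSAID premedication and/or, where 5.2.3 requires it. Section 5.2.7 mentions patients in a Part 2, which this trial does not have.

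**The concern.** These are operative safety instructions for an agent with reported cytokine release syndrome: Section 5.2.4 counts four Grade 2 and two Grade 3 events as of May 2020. Site staff should be able to follow them as written.

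The medication check exists so that acetaminophen and an NSAID are not given longer than needed. That limits their own toxicity and keeps liver findings interpretable, since Section 5.2.6 says that CDX-1140 itself raises liver tests in the first 24 to 48 hours. A check tied to a day before the drug is given cannot do this.

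The observation period decides who is kept for 24 hours. If one sentence says 2 hours and another assumes 4 to 6, two staff members could handle the same unresolved reaction differently.

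**Working it through.** **1. Check the calendar against the plan's own statement.** Inputs from Section 5.2.2: CDX-301 Monday to Friday, then CDX-1140 4 (+/- 1) days after the last dose. The protocol counts in weeks, so cycle days are a construction here: day 1 is the Monday of the first CDX-301 dose.

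- Last CDX-301 dose: day 5 (Friday).
- First CDX-1140: 5 + 4 = day 9, a Tuesday in Week 2. This reproduces the usual weekday given in Section 5.2.2 and the week in the Section 4.2.2 calendar.
- With the window: 5 + 3 = day 8 to 5 + 5 = day 10.
- Second CDX-1140, nominal: 9 + 28 = day 37, a Tuesday in Week 6, again as in the calendar.

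**2. Place Cycle 1 Day 2 on it.**

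- Gap to the first infusion: 9 - 2 = 7 days; with the window, 8 - 2 = 6 to 10 - 2 = 8 days.
- If CDX-301 runs to its latest permitted dose (10 days after the first, day 11), the infusion can be as late as 11 + 5 = day 16, and the gap is 16 - 2 = 14 days.
- The visit that does follow the first infusion is day 10 (range 9 to 11); nominally, day 38 follows the second.

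**3. Count the infusions left without a named check.** Section 8.2 has 23 subjects on Arm 1, with two infusions each in the first cycle: 23 x 2 = 46 at most. This is a maximum because Section 5.2.5 makes the second dose conditional on recovery from toxicity. (It equals the total sample size only by coincidence.)

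- Literal reading: Cycle 1 Day 2 follows none of the 46.
- Charitable reading, with days counted from the first CDX-1140 infusion: it follows at most 23 of the 46, and still none in a repeat cycle.

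**4. Set the observation statements side by side (all in Section 5.2.4).**

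| Text | Period | What it governs |
|---|---|---|
| General rule, stated twice | 2 hours | All subjects, each infusion |
| Grade 2 instruction | 4 to 6 hours, referred to but not set | Start of 24-hour observation if unresolved |
| Grade 3 or higher | None needed | 24 additional hours or until resolution, regardless of how the reaction resolves |

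The discrepancy is 4 - 2 = 2 to 6 - 2 = 4 hours. A Grade 2 event that begins soon after the infusion and is still present at 3 hours has outlasted a 2-hour period but not a 4 to 6 hour one. The two texts therefore give different instructions for the same subject. Grade 3 and higher reactions are unaffected.

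**The case against.** **On the visit.** The sentence sits in a list about medication after each infusion, and nobody can judge whether to continue a drug not yet started. Staff would most likely use the day-after visit, which Sections 4.2.2 and 5.2.2 already require and which resets with each repeat cycle. This stands, and it is why the practical effect is small. It does not make the sentence right: even read charitably, it names one visit for a medication required after every infusion.

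**On observation.** Subjects with an event during the 2 hours are to be monitored further as clinically appropriate, Grade 2 subjects are watched at the bedside until symptoms resolve, and the reaction guidance may be adapted to local standards. All true, and it limits the consequence. None of it says which period the Grade 2 instruction means.

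**Stronger readings that the documents do not support.**

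- A reader might infer that 24 hours in 5.2.6 contradicts 24 to 48 hours in 5.2.3. It lies within that range, and the and/or NSAID wording is a loose back-reference to 5.2.3. Both are editorial.
- A reader might infer that required medication distorts the grading of infusion reactions, and want a rule to disregard it. Section 5.2.4 assigns grading to CTCAE version 5.0, and the 6-hour exception in Section 7.2 applies with or without treatment. An added rule could disturb DLT grading, so none is proposed.
- A reader might infer an effect on the 1-of-6 gate or the 4-of-23 rule. DLTs are defined in Section 7.2, which uses neither the Day 2 visit nor the post-infusion observation period.

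**Conclusion.** The point holds as a minor inconsistency in two safety instructions. The medication check is placed 6 to 8 days before the first CDX-1140 infusion on the usual schedule, and the wording leaves out the second infusion and repeat cycles. The Grade 2 instruction relies on a period 2 to 4 hours longer than the one that its own section sets.

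The day counts assume that a cycle starts with the first CDX-301 dose, as Sections 4.2.2 and 5.2.2 imply. The reference to Part 2 suggests text carried over from another protocol, but that is an inference and the point does not depend on it. The existing day-after visit and bedside monitoring keep the practical effect small. No effect on DLT scoring, either safety rule or the efficacy analysis follows.

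**What to change.** - **Sections 5.2.3 and 5.2.7:** replace the reference to Cycle 1 Day 2 with *the visit one day after each CDX-1140 infusion*. The visit already exists, so this adds no visit, test or CRF field.
- **Section 5.2.4, Grade 2 instruction:** refer to *the 2-hour observation period*. This is the only length that the section sets, and it gives the earlier, more protective trigger for an event already under way. The cost is some additional extended observation: an event unresolved at 2 hours, rather than at 4 to 6, starts observation for 24 hours or until it resolves. Because these subjects are already kept until symptoms resolve, the added burden is small but not zero.
- **Editorial only:** in Section 5.2.6, align the 24-hour duration and the and/or NSAID wording with 5.2.3; in Section 5.2.7, delete the words that limit the growth-factor caution to patients in Part 2.

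All of these can go into the next amendment.

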5.2.4 Potential Toxicities and Toxicity Management

Potential toxicity and guidance for the management of toxicity is summarized below. However, the CDX-1140 and CDX-301 Investigator Brochures (IB) are the Single Reference Safety Documents that provide complete and relevant information about the known safety profile of CDX-1140 and CDX-301.

CDX-301

CDX-301 was generally well-tolerated in all prior studies, including our prior study of CDX-301 and SBRT for advanced NSCLC, which utilized the same CDX-301 dose/schedule as the present trial. The most frequently observed toxicities related to CDX-301 have been asymptomatic lymphadenopathy and mild injection site reactions.

Injection site reactions have been infrequent and mild with CDX-301. No injection site reactions were observed in our recent trial combining CDX-301 and SBRT (29 subjects, 180 injections). Generally mild to moderate injection site reactions were reported in studies using AMG949. Pre-medication with diphenhydramine has been reported to be effective in the prevention of pruritic and erythemic reactions⁹³ and may be considered for subjects who experience local reactions after treatment with CDX-301. Injection site reactions may also be treated with analgesics (i.e., Tylenol). If there is injection site pain, a numbing cream such as Emla cream can be used prior to administration of CDX-301. Patients will be monitored for 30 minutes following each CDX-301 injection.

Leukocytosis, especially monocytosis, is expected during administration of CDX-301. Hematological parameters, including WBC and differential, should be monitored in subjects receiving CDX-301. CDX-301 should not be administered if marked leukocytosis, e.g. WBCs greater than 50,000 cells/mm³, is observed.

CDX-1140

The CDX1140-01 study was the first clinical trial with CDX-1140, and therefore there is limited clinical experience to define expected toxicities. Management of drug-related adverse events and serious adverse events should be in accordance with the institution's standard of care and guidelines for managing immune related toxicities⁹⁴.

CDX-1140 infusion should take place in a monitored setting that has ready access to an intensive care unit in case of a severe infusion reaction. All subjects should be monitored for 2 hours after each administration of CDX-1140; patients who experience any treatment-related adverse events during the observation period should be further monitored as clinically appropriate. CDX-1140 will be administered once every four weeks. CDX-1140 will be administered intravenously over 90 minutes using a 0.22 micron in-line filter. The dose of study treatments will be calculated based on actual weight at screen and may remain constant throughout the study, unless greater than 10% change in weight is observed. The infusion duration can be increased by 30-minute intervals up to 180 minutes if warranted due to prior infusion reactions.

In the phase I trial testing CDX-1140, infusions were generally well-tolerated. Drug-related adverse events have been observed in the post-infusion period, typically within 24-48 hours after completing the infusion. Symptoms have included fever, fatigue, nausea, chills, and arthralgias. As of May 28th, 2020, there were 4 grade 2 and 2 grade 3 cytokine release syndrome adverse events. These adverse events were treated with corticosteroids, and in one case, tocilizumab. It is therefore recommended that medication to treat infusion reactions, including severe infusion reactions/cytokine release syndrome, be readily available at the time of the study drug infusion. All patients should be monitored for 2 hours after each administration of CDX-1140; patients who experience any treatment-related adverse events during the observation period should be further monitored as clinically appropriate.

Recommendations for the management of peri-infusional reactions are provided below and may be modified based on local treatment standards and guidelines, as appropriate. Infusion reactions should be graded according to NCI-CTCAE (Version 5.0) guidelines, <http://ctep.cancer.gov>. Serum should be obtained at the time of an infusion reaction/cytokine release syndrome. Patients who experience a grade 4 infusion reaction or a grade 3 infusion reaction lasting > 6 hours will permanently discontinue CDX-1140, and the adverse event will be considered a DLT.

- For Grade 1 symptoms (Mild transient reaction; infusion interruption not indicated; intervention not indicated):
 - Remain at bedside and monitor patient until recovery from symptoms.
- For Grade 2 symptoms (infusion interruption indicated but responds promptly to symptomatic treatment [e.g., antihistamines, nonsteroidal anti-inflammatory drugs, narcotics, corticosteroids, i.v. fluids]; prophylactic medications indicated for \leq 24 hours):
 - Stop the CDX-1140 infusion, begin an i.v. infusion of normal saline, and treat the patient with diphenhydramine 50 mg i.v. (or equivalent) and/or 500 to 1000 mg paracetamol/acetaminophen; remain at bedside and monitor patient until resolution of symptoms. Corticosteroid therapy may also be administered as appropriate. If the infusion is interrupted, then restart the infusion at 50% of the original infusion rate when symptoms resolve; if no further complications ensue after 30 minutes, the rate may be increased to 100% of the original infusion rate. Monitor patient closely. If symptoms recur, then no further CDX-1140 will be administered at that visit. The amount of study drug infused must be recorded on the case report form (CRF). Patients who experience an adverse event, including an infusion reaction of Grade 2, during the 4 to 6 hour observation period that does not resolve during this time should be observed for 24 hours or until the adverse event resolves with vital sign measurements every 4 hours and additional evaluations as medically indicated for the management of the adverse event.
- For Grade 3 or Grade 4 symptoms (Grade 3: prolonged [i.e., not rapidly responsive to symptomatic medication and/or brief interruption of infusion]; recurrence of symptoms following initial improvement; hospitalization indicated for other clinical sequelae [e.g., renal impairment, pulmonary infiltrates]. Grade 4: life-threatening consequences; urgent intervention indicated):
 - Immediately discontinue infusion of CDX-1140. Begin an i.v. infusion of normal saline, and treat the patient as follows: Recommend bronchodilators, epinephrine 0.2 to 1 mg of a 1:1,000 solution for subcutaneous administration or 0.1 to 0.25 mg of a 1:10,000 solution injected slowly for i.v. administration, and/or diphenhydramine 50 mg i.v. with methylprednisolone 100 mg i.v. (or equivalent), as needed. Tocilizumab should be considered for patients with severe or prolonged infusion reactions/cytokine release syndrome who are not responding to appropriate therapy.

Subjects with peri-infusional reactions should be monitored until the Investigator is comfortable that the symptoms will not recur. Investigators should follow their institutional guidelines for the treatment of anaphylaxis. Patients who experience an

infusion reaction of Grade ≥ 3 , regardless of resolution, will be observed for 24 additional hours or until the adverse event resolves with vital sign measurements every 4 hours and additional evaluations as medically indicated for the management of the adverse event. In the case of late-occurring hypersensitivity symptoms (e.g., appearance of a localized or generalized pruritus within 1 week after treatment), symptomatic treatment may be given (e.g., oral antihistamine, or corticosteroids). CDX-1140 will be permanently discontinued for patients with Grade 4 infusion reactions or Grade 3 infusion reactions lasting more than 6 hours.

5.2.5 Dose Modifications

CDX-301

There will be no CDX-301 dose modifications. If discontinued, CDX-301 will not be reinstated. CDX-301 should not be administered if marked leukocytosis, e.g., WBCs greater than 50,000 cells/mm³, is observed. Any \geq Grade 3 injection site reactions thought related to CDX-301 warrant discontinuation of CDX-301 treatment and will be considered a DLT. If CDX-301 is discontinued due to a DLT, treatment with CDX-1140 may continue in the absence of a CDX-1140-related DLT.

CDX-1140

CDX-1140 dose modifications are not allowed. The second CDX-1140 infusion should only be administered if the subject is receiving \leq 10 mg/day prednisone or equivalent for treatment of drug related toxicity, and all toxicity related to prior treatment (including laboratory abnormalities) has resolved to \leq grade 1, with the following exceptions:

- Subjects may receive treatment in the presence of grade 2 fatigue
- Subjects who have not experienced a grade 3 drug-related skin AE may receive treatment in the presence of grade ≤ 2 skin toxicity
- Subjects with baseline grade 1 AST/ALT or total bilirubin elevation may receive treatment in the presence of grade 2 AST/ALT or total bilirubin elevation
- Grade 2 drug-related pulmonary toxicity, diarrhea, or colitis, must have resolved to baseline before treatment is received
- Patients with drug-related endocrinopathies adequately controlled with only physiologic hormone replacement may receive treatment
- Asymptomatic lymphopenia
- Clinically asymptomatic increased amylase or lipase. The medical monitor should be consulted in the event of grade 4 elevations in amylase or lipase.

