- Immunosuppressive agents and the use of systemic corticosteroids are permitted in the context of treating AEs. Subjects receiving corticosteroids for treatment of drug-related AEs must be at \leq 10 mg/day prednisone or equivalent prior to re- initiation of study therapy.
- Subjects are permitted the use of topical, ocular, intra-articular, intranasal, and inhalational corticosteroids (with minimal systemic absorption).
- Vaccinations:
 - Non-study vaccinations are prohibited until at least 28 days after the last dose of CDX-301. Otherwise, any vaccination containing live, attenuated, or inactivated virus may be permitted if clinically indicated. However, this must be discussed with the Principal Investigator prior to administration and may require a study drug washout period prior to and after administration of the vaccine. Inactivated influenza vaccination is permitted on study without restriction.
 - Some of the systemic adverse events attributed SARS-CoV2 vaccines, such as fever, fatigue, arthralgias, and myalgias, overlap with the adverse events associated with CDX-1140. Administration of the SARS-CoV2 vaccine in close temporal association with CDX-1140 may confound causality assessments for any accompanying adverse events. Therefore, administration of the SARS-CoV2 vaccination and CDX-1140 should be separated by at least 1 week, if possible. For CDX-301, if possible, the vaccine should be administered either at least 1 week prior to the initiation of CDX-301 or at least 3 weeks after the first dose in a cycle, and if eligible for another cycle of treatment, at least 1 week prior to the next cycle. The recommendation is based on the biological activity of CDX-301, which induces a transient increase in hematopoietic cells, including dendritic cell, that peaks at approximately 2 weeks from the initiation of treatment and then rapidly declines. No data is available on the potential impact of CDX-1140 or CDX-301 on the immunogenicity or adverse event profile of the SARS-CoV2 vaccines, therefore decisions to vaccinate patients while participating in this study will be individualized and based on the judgement of the treating investigator.

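### Section 5.2.5 requires return to baseline before the second CDX-1140 infusion only after Grade 2 pulmonary toxicity, diarrhea or colitis; read literally, a Grade 3-4 event meets a looser standard

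*Combined protocol and SAP*

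**What the plan says.** Section 5.2.5 allows the second CDX-1140 infusion when two things hold. The subject must be on no more than 10 mg/day of prednisone or equivalent for drug-related toxicity. In addition, "all toxicity related to prior treatment (including laboratory abnormalities) has resolved to" Grade 1 or less, subject to a list of exceptions. Most items in that list relax the rule. One tightens it: "Grade 2 drug-related pulmonary toxicity, diarrhea, or colitis, must have resolved to baseline before treatment is received".

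The dose itself cannot be lowered: "CDX-1140 dose modifications are not allowed".

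Other provisions that touch on further CDX-1140 are:

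- Section 5.2.5, under CDX-301: "If CDX-301 is discontinued due to a DLT, treatment with CDX-1140 may continue in the absence of a CDX-1140-related DLT".
- Section 5.2.4, on infusion reactions: "CDX-1140 will be permanently discontinued for patients with Grade 4 infusion reactions or Grade 3 infusion reactions lasting more than 6 hours".
- Section 5.2.7: "Subjects receiving corticosteroids for treatment of drug-related AEs must be at" 10 mg/day of prednisone or less before study therapy restarts.
- Section 4.2.2, on later cycles: "CDX-1140 may be omitted from retreatment cycles for subjects with prior DLT or intolerable toxicity attributed to CDX-1140". Section 5.2.2 is permissive in the same way.

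**The concern.** A re-dosing rule should be at least as strict after a severe event as after a moderate one. Here the stricter resolution standard is tied to Grade 2, and no item in the list mentions Grade 3 or 4 events of the same types. The skin item runs in the expected direction: "Subjects who have not experienced a grade 3 drug-related skin AE may receive treatment in the presence of grade" 2 or lower skin toxicity, so a past Grade 3 skin event takes a permission away.

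The toxicity in question is a serious one. Section 2.5 names pneumonitis, with cytokine release syndrome, as the most common serious adverse events of CDX-1140. Section 5.2.6 reports four severe cases on monotherapy. Two patients were intubated. All four received high-dose steroids, and two later died of documented or presumed infection. Three of the four cases began in the first week of treatment. Section 5.2.2 places the second infusion 4 weeks, plus or minus 3 days, after the first, which is 25 to 31 days. An early case would therefore usually be known when the second dose is considered, and this line is the written criterion the team would apply.

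**Working it through.** The plan gives no figure to reproduce. The check is a comparison of the provisions.

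**1. The two standards, taking 'Grade 2' as the worst grade reached**

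| Worst grade of the pulmonary, diarrhea or colitis event | Must resolve to | Prednisone limit |
|---|---|---|
| Grade 2 | Baseline | 10 mg/day |
| Grade 3 or 4 | Grade 1 or less | 10 mg/day |

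The steroid limit is the same in both rows, so the whole difference is baseline against Grade 1 or less.

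**2. When the difference matters**

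- Baseline Grade 1: returning to baseline means reaching Grade 1, so the rows agree.
- Baseline Grade 0, event fully resolved: both rows are met.
- Baseline Grade 0, residual Grade 1: the Grade 2 row forbids the infusion and the Grade 3-4 row allows it. This is the only case where they differ.

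Section 3.2 excludes ongoing pneumonitis and any history of non-infectious pneumonitis. For pneumonitis itself, a Grade 0 baseline is therefore the normal situation, and the gap narrows to subjects with residual Grade 1.

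**3. Does another provision close the gap?**

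- *Section 7.2.* Most Grade 3 or higher non-hematological events attributed to study therapy within 8 weeks of starting initial therapy are DLTs. The section does not say that a DLT ends CDX-1140 for that subject. Section 8.2 attaches consequences to the trial, not to the subject.
- *Section 5.2.5, DLT clause.* It implies that a CDX-1140-related DLT bars further CDX-1140, but it is written only for subjects whose CDX-301 was stopped for a DLT.
- *Section 7.2, diarrhea exception.* Grade 3 diarrhea that falls to Grade 2 or less within 72 hours is not a DLT. Even if every DLT barred re-dosing, the gap would stay open for this event.
- *Section 5.2.4.* The explicit permanent stop covers infusion reactions only.
- *Section 5.2.7.* It repeats the steroid limit and adds no bar by event or grade.
- *Sections 4.2.2 and 5.2.2.* Leaving CDX-1140 out is optional and concerns later cycles.

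None of these states a general rule that covers a Grade 3-4 event before the second infusion.

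**4. Context on pneumonitis (not a measure of the gap)**

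- Inputs: 4 severe monotherapy cases (section 5.2.6); 55 monotherapy and 31 combination patients (section 2.5); 23 Arm 1 subjects (section 8.2). Assumptions: the four cases belong to the same data cut as the 55, and no case being named with the combination means 0 of 31.
- Monotherapy: 4/55 = 7.3%, exact 95% CI 2.0% to 17.6%. Doses were mixed; 23 of these patients had received 1.5 mg/kg.
- Combination: 0/31, exact upper 95% limit 1 − 0.025^(1/31) = 11.2%.
- Expected severe cases in 23 subjects: 23 × 0.0727 = 1.7 (23 × 0.0202 = 0.5 to 23 × 0.1759 = 4.0) at the monotherapy rate; 0 to 23 × 0.1122 = 2.6 over the combination interval.

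These count severe pneumonitis. A subject exposed to the gap must also recover to exactly Grade 1, be at 10 mg/day of prednisone or less when the dose is due, and be judged fit for re-dosing. The documents give none of those proportions.

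**The case against.** The strongest reply is that the inverted order is only one way to read the line. Section 5.2.5 looks at the state to which a toxicity has resolved. A Grade 3 event that improves to Grade 2 is at that moment a Grade 2 toxicity, and on that view the line requires baseline. A reader may also simply supply 'or higher'. Both readings are possible and probably nearer to the intent, but the text states neither, and a safety criterion should not depend on which one a physician chooses.

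A second reply is that Grade 3 or higher is mainly DLT territory. In cycle 1 all CDX-301 is scheduled before any CDX-1140, so the DLT clause in 5.2.5 seems to presuppose that a CDX-1140-related DLT ends CDX-1140. It would make little sense to apply that only to subjects who also lost CDX-301. This stands as evidence of intent. It does not make a general rule, and it does not reach the exempted diarrhea.

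Third, there are safeguards. The conditions are necessary, not sufficient, so a physician may withhold the dose. Section 11.2 sends serious events to the principal investigator and treating physician within 24 hours. The monitoring committee in section 10.4 reviews Grade 3 or higher events every two months, though possibly after an individual's second dose. Section 5.2.4 refers to guidelines for immune-related toxicity and to the Investigator Brochures. Those sources may contain a stopping rule; they are not available here, so the finding is confined to what the protocol itself states.

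A reader might infer that the protocol sends patients back to full-dose CDX-1140 after severe pneumonitis, or that a permanent stop in every cycle is plainly required. The documents support neither. They leave the decision to clinical judgment, and sections 4.2.2 and 5.2.2 deliberately make omission optional. Mandatory discontinuation would be a new clinical rule, not a correction of this line.

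**Conclusion.** The point holds as a wording defect with a safety consequence. On its literal reading, section 5.2.5 asks less after a Grade 3-4 pulmonary event, diarrhea or colitis than after a Grade 2 one, and no other provision in the protocol generally reverses that.

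Its reach is limited to subjects with a Grade 0 baseline and residual Grade 1 toxicity at the time of the second infusion. The number affected cannot be estimated. It would be wrong to read the 1.7 expected pneumonitis cases as the number exposed: that figure rests on monotherapy data at mixed doses and counts events, not re-dosing decisions. The evidence of serious harm in the documents concerns pneumonitis; none is offered for diarrhea or colitis.

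The conclusion assumes that 'Grade 2' refers to the worst grade reached. If the sponsor already means Grade 2 or higher, the change only writes that down. Sample size, power and the primary analysis are not affected. The change is worth making because the toxicity can be grave and the correction is small.

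**What to change.** In section 5.2.5, insert 'or higher' directly after 'Grade 2' in the line on drug-related pulmonary toxicity, diarrhea and colitis, and leave the rest of the line as it is. Grades 2, 3 and 4 then share the return-to-baseline condition.

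Optional, for the sponsor to decide: state whether CDX-1140 is permanently discontinued after Grade 3-4 drug-related pneumonitis. If such a rule is added, tie it to the event and not to the DLT definition. Section 7.2 counts only events within 8 weeks of starting initial therapy and would miss a case in a retreatment cycle. Sections 4.2.2 and 5.2.2 should then refer to it.

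Cost: two words, plus one sentence and two cross-references if the option is taken. A few subjects may receive the second dose later or lose it. The sample size, visit schedule and DLT definition stay as they are. One side effect should be noted: section 7.2 counts a delay of more than 2 weeks for drug-related toxicity that is not improving as a DLT. A longer wait for baseline could therefore, rarely, add a DLT in a subject not already counted, for example after the exempted Grade 3 diarrhea.
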